7.4.1 Analysis of WI-NRS and AI-NRS

The primary endpoint of mean change from Baseline to Week 4 in WI-NRS will be analyzed using analysis of covariance (ANCOVA) models.

In addition, the continuous efficacy endpoints WI-NRS, AI-NRS will be summarized using descriptive statistics at Baseline, Week 1, Week 2, Week 3, Week 4, Week 5, Week 6, Week 7, and Week 8 for actual values and change from Baseline values.

The difference in treatment groups in change from Baseline values at post-baseline visits will be analyzed using a mixed model with repeated measures to account for within subject variability and including visit (Baseline vs. Week 1, Week 2, Week 3, Week 4, Week 5, Week 6, Week 7, Week 8), treatment group, visit-by-treatment interaction, and Baseline value as explanatory variables. The subject variability will be modelled using a compound symmetry covariance matrix. Other types of covariance structure may be applied should they provide a better model fit.

The frequency and rate of WI-NRS and AI-NRS responders at Week 1, Week 2, Week 3, Week 4, Week 5, Week 6, Week 7, Week 8 (\geq 4 point change from Baseline in WI-NRS and AI-NRS) and other responder endpoints (any improvement from Baseline in WI-NRS and AI-NRS, defined as \geq 1 point change from Baseline) will be reported and compared between treatment groups using a logistic regression model by week. Generalized estimating equations to account for repeated measures and within-subject variability may also be applied. Responder status varies by outcome measure, endpoint, and visit. That is, a subject can be considered a responder at one visit, but not the next for a specific measure. Similarly, a subject can be considered a responder for one measure but not another at the same visit.

Additionally, daily WI-NRS and AI-NRS scores will be presented in by-subject data listings.

7.4.2 Analysis of Primary Endpoint of Change from Baseline to Week 4 in Weekly Average WI-NRS

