| | | LSM Difference (SE) | xx.x (xx.xxx) | xx.x (xx.xxx) | xx.x (xx.xxx) | N/A |
| | | 90% UCL Adjusted [5] | XX.X | XX.X | XX.X | N/A |
| | | p-value | X.XXXX | X.XXXX | X.XXXX | N/A |
| | 20.0 v 5.0 | | | | | |
| | | LSM Difference (SE) | N/A | xx.x (xx.xxx) | N/A | N/A |
| | | 90% UCL Adjusted | N/A | XX.X | N/A | N/A |
| | | p-value | N/A | X.XXXX | N/A | N/A |
| | | | | | | |

Table 14.2.2.1 Mean Change in WI-NRS from Baseline to Week 4 - ANCOVA (mITT Population)

[1] CFB = Change from Baseline.

[2] ANCOVA = Analysis of Covariance model.

[3] Model contains treatment group and baseline WI-NRS as explanatory variables, where baseline WI-NRS = (Sum of daily WI-NRS scores from Day -7 to Day -1) / (Total number of WI-NRS diaries entered from Day -7 to Day -1) and at least one WI-NRS daily score is reported between Days -7 and -1. Multiplicity is adjusted for with the Dunnett Testing Method using a one-sided familywise error rate of 0.10. All subjects who meet mITT criteria are included and no data is excluded based on rescue medication use. [4] LSM = Least Squares Mean. SE = Standard Error.

[5] UCL = Upper Confidence Limit for one-sided confidence inteval.

Source: Listing XXXX

PROGRAM NAME: XXXXXXXXXX

DATE: HH:MM/DDMMMYYYY

Programming Note:

Repeat for 14.2.2.2 Mean Change in WI-NRS from Baseline to Week 4 – ANCOVA for PP Population •

• Footnote [3] will be same as in 14.2.2.1, except changing the last statement to "All subjects who meet PP criteria are included."

Table 14.2.2.3.1 Mean Change in WI-NRS from Baseline to Weeks 1 Through 8 – Primary Analysis (mITT Population)

| | | | B244 O.D. 5.0 | B244 O.D. 20.0 | Pooled B244 | Vehicle |
|------------------------|----------------|---------------------|---------------|----------------|---------------|---------------|
| Visit | Statistic Type | Statistic | (N=xx) | (N=xx) | (N=xx) | (N=xx) |
| Week 1 CFB [1] | MMRM [2,3] | n | XX | XX | XX | XX |
| | | LSM (SE) [4] | xx.x (xx.xxx) | xx.x (xx.xxx) | xx.x (xx.xxx) | xx.x (xx.xxx) |
| | | 95% CI | (xx.x, xx.x) | (xx.x, xx.x) | (xx.x, xx.x) | (xx.x, xx.x) |
| | v. Vehicle | LSM Difference (SE) | xx.x (xx.xxx) | xx.x (xx.xxx) | xx.x (xx.xxx) | N/A |
| | | 95% CI | XX.X | XX.X | XX.X | N/A |
| | | p-value | X.XXXX | X.XXXX | X.XXXX | N/A |
| | 20.0 v 5.0 | LSM Difference (SE) | N/A | X.XXXX | N/A | N/A |
| | | 95% CI | N/A | xx.x (xx.xxx) | N/A | N/A |
| Repeat for Weeks 2 – 8 | | p-value | N/A | XX.X | N/A | N/A |

[1] CFB = Change from Baseline.

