[2] MMRM = Mixed Model Repeated Measures.

[3] Model uses a compound symmetry covariance structure and contains visit, treatment group, visit-by-treatment interaction, and baseline WI-NRS as explanatory variables, where baseline WI-NRS = (Sum of daily WI-NRS scores from Day -7 to Day -1) / (Total number of WI-NRS diaries entered from Day -7 to Day -1) and at least one WI-NRS daily score is reported between Days -7 and -1 and for the corresponding week. All subjects who meet mITT criteria are included and no data is excluded based on rescue medication use. [4] LSM = Least Squares Mean. SE = Standard Error.

Source: Listing XXXX

PROGRAM NAME: XXXXXXXXXX

DATE: HH:MM/DDMMMYYYY

- Repeat for 14.2.2.3.2 Mean Change in WI-NRS from Baseline to Weeks 1 Through 8 Primary Analysis Sensitivity for mITT Population
 Footnote [3] will be same as in 14.2.2.3.1, except changing "one WI-NRS daily score is" to "four WI-NRS daily scores are"
 - Repeat for 14.2.2.3.3 Mean Change in WI-NRS from Baseline to Weeks 1 Through 8 Sub-Analysis for mITT Population
 - Footnote [3] will be same as in 14.2.2.3.1, except changing the last statement to "Excludes data collected from the week of first on-treatment rescue medication use through the end of the study. Data collected prior to the week of first on-treatment rescue medication use will be included."
- Repeat for 14.2.2.3.4 Mean Change in WI-NRS from Baseline to Weeks 1 Through 8 Sub-Analysis Sensitivity for mITT Population
 - Footnote [3] will be same as in 14.2.2.3.1, except changing "one WI-NRS daily score is" to "four WI-NRS daily scores are" and changing the last statement to "Excludes data collected from the week of first on-treatment rescue medication use through the end of the study. Data collected prior to the week of first ontreatment rescue medication use will be included."
- Repeat for 14.2.2.3.5 Mean Change in WI-NRS from Baseline to Weeks 1 Through 8 for PP Population Primary Analysis
 - Footnote [3] will be same as in 14.2.2.3.1, except changing the last statement to "All subjects who meet PP criteria are included."
- Repeat for 14.2.2.3.6 Mean Change in WI-NRS from Baseline to Weeks 1 Through 8– Primary Analysis Sensitivity for PP Population
 - Footnote [3] will be same as in 14.2.2.3.1, except changing "one WI-NRS daily score is" to "four WI-NRS daily scores are" and changing the last statement to "All subjects who meet PP criteria are included."

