- Repeat for 14.2.2.8.11 Proportion of Subjects with Any Improvement in WI-NRS from Baseline to Weeks 1 Through 8 Non-Responder Imputation (NRI) Analysis for PP
 Population
 - Footnotes [1,2,3] will be same as in 14.2.2.6.11, except changing "WI-NRS" to "AI-NRS"
- Repeat for 14.2.2.8.12 Proportion of Subjects with Any Improvement in WI-NRS from Baseline to Weeks 1 Through 8 Non-Responder Imputation (NRI) Analysis Sensitivity for PP Population
 - Footnotes [1,2,3] will be same as in 14.2.2.6.12, except changing "WI-NRS" to "AI-NRS"

Table 14.2.2.9.1 Mean Change in 5-D Pruritus Scale Total Score from Baseline to Weeks 2, 4, and 8 – Primary Analysis (mITT Population)

| Visit | Statistic Type | Statistic | B244 O.D. 5.0 (N=xx) | B244 O.D. 20.0 (N=xx) | Pooled B244 (N=xx) | Vehicle (N=xx) |
|--------------------------|----------------|--|---|---|---|-------------------------------------|
| Week 2 CFB [1] | MMRM [2,3] | n LSM (SE) [4] 95% CI | xx xx.x (xx.xxx) (xx.x, xx.x) | xx xx.x (xx.xxx) (xx.x, xx.x) | xx xx.x (xx.xxx) (xx.x, xx.x) | xx xx.x (xx.xxx) (xx.x, xx.x) |
| | v. Vehicle | LSM Difference (SE) 95% CI p-value | xx.x (xx.xxx) (xx.x, xx.x) x.xxxx | xx.x (xx.xxx) (xx.x, xx.x) x.xxxx | xx.x (xx.xxx) (xx.x, xx.x) x.xxxx | N/A N/A N/A |
| Repeat for Weeks 4 and 8 | 20.0 v 5.0 | LSM Difference (SE) 95% CI p-value | N/A N/A N/A | xx.x (xx.xxx) (xx.x, xx.x) x.xxxx | N/A N/A N/A | N/A N/A N/A |

[1] CFB = Change from Baseline.

[2] MMRM = Mixed Model with Repeated Measures.

[3] Model uses a compound symmetry covariance structure and contains visit, treatment group, visit-by-treatment interaction, and baseline 5-D Pruritus total score as explanatory variables. All subjects who meet mITT criteria are included and no data is excluded based on rescue medication use.

[4] LSM = Least Squares Mean. SE = Standard Error.

Source: Listing XXXX

PROGRAM NAME: XXXXXXXXXX

DATE: HH:MM/DDMMMYYYY

- Repeat for 14.2.2.9.2 Mean Change in 5-D Pruritus Scale Total Score from Baseline to Weeks 2, 4, and 8 Sub-Analysis for mITT Population
 - Footnote [3] will be same as in 14.2.2.9.1, except changing the last statement to "Excludes visit data collected on/after date of first on-treatment rescue medication use through the end of the study."
- Repeat for 14.2.2.9.3 Mean Change in 5-D Pruritus Scale Total Score from Baseline to Weeks 2, 4, and 8 Primary Analysis for PP Population

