 Footnote [3] will be same as in 14.2.2.9.1, except changing the last statement to "All subjects who meet PP criteria are included."
- Repeat for 14.2.2.9.4 Mean Change in 5-D Pruritus Scale Total Score from Baseline to Weeks 2, 4, and 8 Sub-Analysis for PP Population
 Footnote [3] will be same as in 14.2.2.9.1, except changing the last statement to "All subjects who meet PP criteria are included."
- Repeat for 14.2.2.10.1 Mean Change in EASI Total Score from Baseline to Weeks 2, 4, and 8 Primary Analysis for mITT Population
 Footnote [3] will be same as in 14.2.2.9.1, except changing "5-D Pruritus" to "EASI"
- Repeat for 14.2.2.10.2 Mean Change in EASI Total Score from Baseline to Weeks 2, 4, and 8 Sub-Analysis for mITT Population
 Footnote [3] will be same as in 14.2.2.9.2, except changing "5-D Pruritus" to "EASI"
- Repeat for 14.2.2.10.3 Mean Change in EASI Total Score from Baseline to Weeks 2, 4, and 8 Primary Analysis for PP Population
 - Footnote [3] will be same as in 14.2.2.9.3, except changing "5-D Pruritus" to "EASI"
- Repeat for 14.2.2.10.4 Mean Change in EASI Total Score from Baseline to Weeks 2, 4, and 8 Sub-Analysis for PP Population
 o Footnote [3] will be same as in 14.2.2.9.4, except changing "5-D Pruritus" to "EASI"
- Repeat for 14.2.2.11.1 Mean Change in IGA from Baseline to Weeks 2, 4, and 8 Primary Analysis for mITT Population
 Footnote [3] will be same as in 14.2.2.9.1, except changing "5-D Pruritus total score" to "IGA"

- Repeat for 14.2.2.11.2 Mean Change in IGA from Baseline to Weeks 2, 4, and 8 Sub-Analysis for mITT Population
 o Footnote [3] will be same as in 14.2.2.9.2, except changing "5-D Pruritus total score" to "IGA"
- Repeat for 14.2.2.11.3 Mean Change in IGA from Baseline to Weeks 2, 4, and 8 Primary Analysis for PP Population
 Footnote [3] will be same as in 14.2.2.9.3, except changing "5-D Pruritus total score" to "IGA"
- Repeat for 14.2.2.11.4 Mean Change in IGA from Baseline to Weeks 2, 4, and 8 Sub-Analysis for PP Population
 o Footnote [3] will be same as in 14.2.2.9.4, except changing "5-D Pruritus total score" to "IGA"
- Repeat for 14.2.2.12.1 Mean Change in POEM Total Score from Baseline to Weeks 2, 4, and 8 Primary Analysis for mITT Population
 o Footnote [3] will be same as in 14.2.2.9.1, except changing "5-D Pruritus Scale" to "POEM"
- Repeat for 14.2.2.12.2 Mean Change in POEM Total Score from Baseline to Weeks 2, 4, and 8 Sub-Analysis for mITT Population

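### Cheap improvement, low severity: the repeated-measures models default to compound symmetry, which mis-sizes week-specific standard errors if the SD of change differs by week; the primary ANCOVA is not affected

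*SAP*

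**What the plan says.** SAP 7.4.1 sets the default for the weekly WI-NRS and AI-NRS change scores: "The subject variability will be modelled using a compound symmetry covariance matrix". The next sentence leaves it open: "Other types of covariance structure may be applied should they provide a better model fit". No fit criterion, list of candidates, order or decision time is given.

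The shells carry no such option. Footnote [3] of Table 14.2.2.3.1 (WI-NRS, Weeks 1 to 8) reads "Model uses a compound symmetry covariance structure and contains visit, treatment group, visit-by-treatment interaction, and baseline WI-NRS as explanatory variables", and the programming notes carry it to AI-NRS. Footnote [3] of Table 14.2.2.9.1 (Weeks 2, 4 and 8) reads "Model uses a compound symmetry covariance structure and contains visit, treatment group, visit-by-treatment interaction, and baseline 5-D Pruritus total score as explanatory variables", and the notes carry it to EASI, IGA and POEM, for example "Repeat for 14.2.2.12.1 Mean Change in POEM Total Score from Baseline to Weeks 2, 4, and 8 Primary Analysis for mITT Population". The Addendum shells with worst-observation imputation (14.2.2.3.4a/b, 14.2.2.4.4a/b, 14.2.2.10.2a, 14.2.2.11.2a) do the same. SAP 7.4.3 names no structure.

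The primary test (SAP 7.4.2) is a Week 4 ANCOVA on treatment and baseline, with one value per subject. SAP 7.4 declares secondary and exploratory p-values exploratory.

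**The concern.** Compound symmetry imposes one variance on all visits, so every week receives nearly the same standard error. Where the true SD lies below the average the interval is too wide; where it lies above, the interval is too narrow and the test rejects too often. SDs of change can plausibly grow as follow-up lengthens, or fall back once treatment stops at Week 4. Nothing in the documents supports equal SDs, and nothing contradicts them.

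At stake are the intervals of four of the nine secondary endpoints: mean change in WI-NRS at Week 2, and in AI-NRS, POEM and 5-D at Week 4. The exploratory EASI and IGA mean changes are also affected. So are two observed-data checks on the WI-NRS result, the four-diary sensitivity analysis ("Repeat for 14.2.2.3.2 Mean Change in WI-NRS from Baseline to Weeks 1 Through 8 Primary Analysis Sensitivity for mITT Population") and the rescue-exclusion analysis ("Repeat for 14.2.2.3.3 Mean Change in WI-NRS from Baseline to Weeks 1 Through 8 Sub-Analysis for mITT Population"). In SAP v3.0 these two exist only as repeated-measures tables. The main ANCOVA does not cover the second; its footnote says "All subjects who meet mITT criteria are included and no data is excluded based on rescue medication use".

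**Working it through.** **Inputs.** SD of the Week 4 change 2.5; 160 evaluable per group, 480 in all; 16.7% dropout (SAP 7.1). Two-sided 95% intervals for non-primary tests (SAP 6.3). The plan states no weekly SDs and no figure on covariance, so there is none to reproduce. From its design values, the correct Week 4 standard error of a pairwise difference is 2.5 × √(2/160) = 0.280, and the half-width is 1.96 × 0.2795 = 0.548.

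**Formulas (complete data).** The compound-symmetry variance is the mean of the weekly variances. Ratio of model SE to true SE at week t = √(mean variance) / SD at week t. Test level = 2 × (1 − Φ(1.96 × ratio)).

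**Example, path F** (SDs 1.6, 2.0, 2.3, 2.5, 2.4, 2.3, 2.1, 2.0). The squares sum to 37.56; the mean is 4.695 and its root 2.167. Week 2: 2.167/2.0 = 1.083. Week 4: 2.167/2.5 = 0.867, level 8.9%. The Week 4 half-width would be 0.475 instead of 0.548.

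**Eight-week model (WI-NRS, AI-NRS), assumed SDs:**

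| Path | Weekly SDs | Week 2 ratio | Week 4 ratio | Week 4 level |
|---|---|---|---|---|
| Constant | 2.5 throughout | 1.000 | 1.000 | 5.0% |
| A rising | 2.0, 2.2, 2.4, then 2.5 | 1.088 | 0.958 | 6.1% |
| B rising | 1.6, 2.0, 2.3, then 2.5 | 1.161 | 0.928 | 6.9% |
| C rising | 1.3, 1.8, 2.2, then 2.5 | 1.258 | 0.906 | 7.6% |
| D rising | 1.6, 2.0, 2.3, 2.5, 2.65, 2.8, 2.9, 3.0 | 1.255 | 1.004 | 4.9% |
| E fall-back | 2.0, 2.2, 2.4, 2.5, 2.4, 2.3, 2.1, 2.0 | 1.020 | 0.898 | 7.8% |
| F fall-back | as above | 1.083 | 0.867 | 8.9% |
| G fall-back | 1.6, 2.0, 2.3, 2.5, 2.45, 2.4, 2.3, 2.2 | 1.118 | 0.894 | 8.0% |

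At Week 2 the error is conservative on every unequal path. At worst (path C) the interval is as wide as with 1 − 1/1.258² = 37% fewer subjects.

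**Three-visit model (POEM, 5-D, EASI, IGA), SDs at Weeks 2/4/8 relative to Week 4:**

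| Pattern | Week 4 ratio | Week 4 level |
|---|---|---|
| 0.8/1/1 | 0.938 | 6.6% |
| 0.7/1/1 | 0.911 | 7.4% |
| 0.8/1/1.2 | 1.013 | 4.7% |
| 0.8/1/0.8 | 0.872 | 8.8% |
| 0.8/1/0.9 | 0.904 | 7.7% |
| 0.9/1/0.9 | 0.935 | 6.7% |

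**Simulation check** (600 runs, AR-type correlation 0.85, SDs 1.5, 2.0, 2.3, then 2.5). Week 4 coverage of a 95% interval with complete data: 93.2% under compound symmetry, 94.7% unstructured. With 16.7% outcome-dependent dropout: 91.3% and 93.7%. With equal SDs and the same correlation, compound symmetry covered 94.8 to 95.0%. In these runs the harm came from unequal variances, not from a wrong correlation pattern.

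**Rescue-exclusion check at Week 4** (3,000 runs, no true effect, assumed rescue rates of 20% and 37%). Path B: test level 6.9% and 7.0%. Path F: 8.8% and 9.4%. Constant SD: 4.6 to 4.7%. Unstructured: 4.7 to 4.9% throughout.

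**Would the fit option be used?** With 480 subjects and AR(1) correlation 0.85, the expected gain in twice the log-likelihood for unstructured over compound symmetry is 1,726 to 2,112 on paths A to G. The penalties are 68 (AIC) and 210 (BIC), so a switch is nearly certain. With exchangeable correlation 0.6 on the two mildest paths (A and E), AIC chooses unstructured in at least 99% of runs and BIC in none. If heterogeneous compound symmetry were also a candidate, both criteria would be expected to leave plain compound symmetry.

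**The case against.** The strongest reply is that no decision depends on this. The primary test is an ANCOVA and the secondary p-values are exploratory. That stands, and it sets the severity. It does not make a 95% interval cover at 95%.

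Second, the fit sentence in SAP 7.4.1 already lets the analyst leave compound symmetry. This largely stands for WI-NRS and AI-NRS. A reader might infer from the shells that compound symmetry is locked in. The documents do not go that far: SAP 6.3 presents the shells as expected layout, and SAP 7.4.3 refers the other scales back to section 7.4. But 7.4.3 does not repeat the option, so it is unclear whether it reaches POEM and 5-D, and where it does apply the criterion is missing.

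Third, a reader might infer that the primary result has no robustness check free of compound symmetry. That is not so. Addendum Tables 14.2.2.2a and 14.2.2.2b repeat the Week 4 ANCOVA with worst-observation imputation from rescue use onward, the second requiring four diary scores. Table 14.2.2.2c repeats it in all randomized subjects with last-observation imputation. The per-protocol ANCOVA (14.2.2.2) also excludes subjects over the rescue limit. Only the observed-data versions of the checks depend on the covariance.

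Fourth, every size above rests on assumed SDs. That stands too.

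**Conclusion.** The point holds as a cheap improvement of low severity. If the SD of change varies by week and compound symmetry is kept, the WI-NRS Week 2 standard error is 2 to 26% too large. The Week 4 standard error runs from 1% too large to 13% too small, with a nominal 5% test at 4.7 to 8.9%. These figures assume complete data and the SD paths shown. With constant SDs the error is nil. For WI-NRS and AI-NRS they are upper bounds, since the fit option would probably be taken; POEM and 5-D at Week 4 are the most exposed.

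The words primary analysis in the title of Table 14.2.2.3.1 might suggest that the primary test is affected. It is not: that table is the repeated-measures model, while the primary test is the ANCOVA in Table 14.2.2.1. The responder endpoints, analysed by logistic regression week by week, are also unaffected.

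One slip needs no assumption. The Addendum last-observation shells for AI-NRS (14.2.2.4.9), EASI (14.2.2.10.5) and IGA report Week 4 only, one value per subject, yet name compound symmetry. There is no within-subject covariance to model. This is editorial.

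**What to change.** - In SAP 7.4.1, 7.4.3 and the repeated-measures shells, including the Addendum worst-observation shells, specify an unstructured covariance with a stated degrees-of-freedom method, for example Kenward-Roger.
- Replace the open sentence on model fit with a fixed fallback order used only for non-convergence, for example heterogeneous Toeplitz, then heterogeneous AR(1). The particular order is a choice; what matters is that it is fixed beforehand.
- Delete the covariance wording from the single-week last-observation shells in the Addendum.

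The cost is wording and about one line of code per model, with no new data. The downside is more covariance parameters: 8 × 9/2 = 36 for eight weeks and 3 × 4/2 = 6 for three visits. That is minor with about 480 evaluable subjects.

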7.4.3 Analysis of IGA, EASI, POEM, 5-D Pruritus Scale

The endpoints IGA, EASI, POEM, 5-D Pruritus Scale will be summarized using descriptive statistics and analyzed using a logistic regression model at each respective timepoints. Mean change from Baseline to Week 2, Week 4, and Week 8 in IGA, EASI, POEM, and 5-D Pruritus Scale, as well as IGA and EASI responders, will be analyzed for mITT and PP as described in section 7.4.

Responder status is determined by reaching a certain level of improvement as defined below. Responder status varies by outcome measure, endpoint, and visit. That is, a subject can be considered a responder at one visit, but not the next for a specific measure. Similarly, a subject can be considered a responder for one measure but not another at the same visit. Responder criteria for categorical measures are as follows:

- Proportion of subjects with an IGA 0 (clear) or 1 (almost clear) and \geq 2-point improvement from Baseline will be reported for Week 2, Week 4, and Week 8.
- Proportion of subjects with IGA 0 (clear) or 1 (almost clear) will be reported for Week 2, Week 4, and Week 8.
- Proportion of subjects with any improvement in IGA from Baseline (defined as ≥1 point change from Baseline) will be reported for Week 2, Week 4, and Week 8.
- Proportion of subjects with at least 50%, 75%, and 90% improvement in EASI (EASI-50, EASI-75, and EASI-90, respectively) from Baseline will be reported for Week 2, Week 4, and Week 8.

Each of these outcomes will be compared between treatment groups using a logistic regression model by week. Generalized estimating equations to account for repeated measures and within-subject variability may also be applied.

7.5 Safety Analysis

Safety analyses will be conducted using the Safety population.

7.5.1 Study Drug Exposure

Subject dosing/exposure is recorded in both the ERT (patient diary entries) and EDC (site entries). In case of any discrepancies of the first and/or last exposure date between ERT and EDC, the EDC date will be used. Only ERT records that fall within the first and last dosing dates reported in the EDC (inclusive) will be retained.

Each site participating in the trial will be instructed to assess subject's compliance by weighing the investigational product at the Baseline visit, Week 2 visit, and Week 4 visit and followed every time study medication is dispensed and returned.

At the Week 2 visit, subjects will return any empty bottle (likely Bottle 1 since each bottle should last approximately 10 days and the subject should be on Bottle 2 at the time of visit) to

STATISTICAL ANALYSIS PLAN

Version 3.0 12-Jan-22

the site for weight measurement. At the Week 4 visit, all used and unused bottles will be returned to the site for weight measurements.

The cumulative amount of study drug exposure will be estimated by calculating the difference between the weight of all bottles of drug dispensed and the weight of all bottles returned. Differences will be summed together and reported as Net Weight of Study Drug.

The amount of product used per day will be estimated by dividing the change by the number of days the subject was on treatment. These weights will be compared to the weight of the product that would be used if the subject was compliant with the protocol. Percent compliance will be calculated as follows, with planned study drug use per day defined as 2.8g (0.14 g per pump x 10 pumps per application x 2 applications per day = 2.8 g) and number of days = 28 days:

Percent compliance = $\frac{\text{Net Weight of Study Drug}}{[Planned study drug use per day] * Numbers of days} \times 100$

The expected amount of study drug used over 4 weeks is approximately 0.14 g per pump x 10 pumps per application x 2 applications per day x 28 days of treatment = 78.4 g. The compliance will be calculated for Baseline to Week 4 visit.

The total dispensed and returned IP weights, the Net Weight of Study Drug, and the percent compliance during the treatment period will be summarized by treatment group and pooled B244 treatment and will be presented in a by-subject data listing. Percent compliance will be calculated for all subjects who received study drug, even if they did not return any/all of their study drug kits. Kits not returned will be assumed to be fully used and the return weight will be imputed as 0g. In the listing, the total weight dispensed, returned, net weight, and % compliance will be presented.

Dose compliance for each subject will also be calculated based on the number of daily study drug dosing diaries entered out of the total study drug dosing diaries available (2 study drug dosing diaries available per day x 28 days of treatment = 56 available entries). Only ERT dosing diary records from date of first dose through date of Visit 4-1 will be considered for calculating secondary compliance.

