At the Week 2 visit, subjects will return any empty bottle (likely Bottle 1 since each bottle should last approximately 10 days and the subject should be on Bottle 2 at the time of visit) to the site for weight measurement (without the safety cap) to confirm usage. At this visit, a third bottle of the same treatment group will be labeled as Bottle 3 and will be vortexed, primed, and weighed at the site at the time of dispense without the cap, the cap inserted back on the bottle, and the bottle returned to its carton unused. The subject will be dispensed Bottle 3 to take home and store in the refrigerator until Bottle 2 is empty, at which point Bottle 3 is taken out of the refrigerator and used on the counter until the Week 4 visit. All empty bottles returned to the site will be collected and stored by the site in ambient temperature until return to the drug depot. If the subject is still on Bottle 1 at the Week 2 visit, the site will confirm daily dosing application and retrain the subject on the appropriate use of IP application, and the subject will continue using Bottle 1 until empty, at which point Bottle 2 is taken out of the refrigerator and used on the counter until Bottle 2 is empty, after which Bottle 3 is taken out of the refrigerator and used on the counter until the Week 4 visit. Any bottle currently in use at the time of the Week 2 visit should not be returned to the site.

At the Week 4 visit, all used and unused bottles will be returned to the site for weight measurements and storage at the site in ambient temperature until return to the drug depot.

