[1] Net Weight of Study Drug (g) = (Total Weight Dispensed (g)) – (Total Weight Returned (g)).
 [2] Compliance (%) based on IP Weight = (Net Weight of Study Drug (g)) / (Planned Study Drug Use per Day (g) * Number of Days Expected Use of Study Drug) where Planned Study Drug Used per Day = 2.8g and Number of Days Expected Use of Study Drug = 28 days.

[3] Subjects who administered at least 50% of IP (where Net Weight of Study Drug (g) is at least 50% of the initial product weight (g) (i.e., 0.14 g per pump * 20 pumps per day * 28 days = 78.4 g).

[4] Number of Dosing Diaries Entered = Number of dosing diaries entered with a YES confirming study drug dosing.

[5] Compliance (%) based on Diary Entries = (Number of Dosing Diaries Entered) / (Number of Dosing Diaries Available) where Number of Dosing Diaries Available is the total number of dosing diaries expected from a 28 day treatment (56 diaries).

Source: Listing XXXX

PROGRAM NAME: XXXXXXXXXX
| | | | B244 O.D. 5.0 | B244 O.D. 20.0 | Pooled B244 | Vehicle |
|--------------------------------------|-----------------------|-----------|---------------|----------------|--------------|--------------|
| Local Tolerability Symptom | Day | Statistic | (N=xx) | (N=xx) | (N=xx) | (N=xx) |
| Skin Redness and/or Color Change | Day 1 | n | XX | XX | XX | XX |
| | | Mean (SD) | xx.x (xx.xx) | xx.x (xx.xx) | xx.x (xx.xx) | xx.x (xx.xx) |
| | | Median | XX.X | XX.X | XX.X | XX.X |
| | | Min, Max | XX, XX | XX, XX | xx, xx | XX, XX |
| | Day 2 | n | XX | XX | XX | XX |
| | | Mean (SD) | xx.x (xx.xx) | xx.x (xx.xx) | xx.x (xx.xx) | xx.x (xx.xx) |
| | | Median | XX.X | XX.X | XX.X | XX.X |
| | | Min, Max | XX, XX | XX, XX | XX, XX | XX, XX |
| | Day 2 CFPD | n | XX | XX | XX | XX |
| | | Mean (SD) | xx.x (xx.xx) | xx.x (xx.xx) | xx.x (xx.xx) | xx.x (xx.xx) |
| | | Median | XX.X | XX.X | XX.X | XX.X |
| | | Min, Max | XX, XX | XX, XX | XX, XX | XX, XX |
| | Day 3 | n | XX | XX | XX | XX |
| | | Mean (SD) | xx.x (xx.xx) | xx.x (xx.xx) | xx.x (xx.xx) | xx.x (xx.xx) |
| | | Median | XX.X | XX.X | XX.X | XX.X |
| | | Min, Max | XX, XX | XX, XX | xx, xx | xx, xx |
| | Day 3 CFPD | n | XX | XX | XX | XX |
| | | Mean (SD) | xx.x (xx.xx) | xx.x (xx.xx) | xx.x (xx.xx) | xx.x (xx.xx) |
| | | Median | XX.X | XX.X | XX.X | XX.X |
| | | Min, Max | XX, XX | XX, XX | XX, XX | XX, XX |
| | Day 4 | n | XX | XX | XX | XX |
| | - | Mean (SD) | xx.x (xx.xx) | xx.x (xx.xx) | xx.x (xx.xx) | xx.x (xx.xx) |
| | | Median | XX.X | XX.X | XX.X | XX.X |

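### SAP 7.5.1 divides compliance by a fixed 28 days while the dose counted runs to the actual Week 4 visit, so a completer who misses nothing scores about 93% to 109%

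*SAP*

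**What the plan says.** On weight, SAP 7.5.1 begins with a daily rate: "The amount of product used per day will be estimated by dividing the change by the number of days the subject was on treatment". It compares this with what a compliant subject would use. The percent-compliance formula that follows has "planned study drug use per day defined as 2.8g" "and number of days = 28 days", so its denominator is the product ending "2 applications per day x 28 days of treatment = 78.4 g". Footnote 2 of Table 14.3.5 repeats this: "Planned Study Drug Used per Day = 2.8g and Number of Days Expected Use of Study Drug = 28 days". Neither Table 14.3.5 nor Listing 16.2.5.2 has a row or column for the per-day amount.

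On diaries, the denominator is "2 study drug dosing diaries available per day x 28 days of treatment = 56 available entries". The numerator rule is "Only ERT dosing diary records from date of first dose through date of Visit 4-1 will be considered for calculating secondary compliance".

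Protocol 8.6 has product used up to the clinic visit: "Bottle 3 is taken out of the refrigerator and used on the counter until the Week 4 visit". Protocol Appendix A sets that visit at Day 28 with a window of 2 days either side and schedules an application on it. Protocol 8.7 describes a 28-day course. SAP 7.7 notes that the schedule spans 29 days and trims the dosing diaries to the day before Visit 4. It does not trim the weights.

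**The concern.** The numerator follows the subject's own calendar and the denominator does not. The score therefore moves with visit timing as well as with missed doses. A subject seen late can miss doses and still show full compliance, and a subject seen early cannot reach 100%. For those who stop early, one percentage combines how long they were treated with how well they applied the product while treated.

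Table 14.3.5 is the by-arm summary from which a reader would judge whether the two B244 doses and vehicle were applied equally well. The SAP handles varying interval length elsewhere: 6.5.3 closes the Week 4 itch average at the earlier of Day 28 and the day before Visit 4, and 7.5.4 rescales rescue-medication days by the actual length of each interval.

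**Working it through.** **Inputs.** 0.14 g per pump, 10 pumps per application and 2 applications per day (SAP 7.5.1); Visit 4 at protocol Day 28 ± 2, with Day 0 the day of first dose (Protocol Appendix A, SAP 2.2); diary cut-off at the day before Visit 4 (SAP 7.5.1).

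**The plan's own figures.** 0.14 × 10 = 1.4 g per application; 1.4 × 2 = 2.8 g per day; 2.8 × 28 = 78.4 g; 2 × 28 = 56 diaries. All reproduce.

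**A completer who misses no dose.** Assume two applications on Day 0. With Visit 4 on Day *v*, the period from Day 0 to the day before the visit has *v* days. Diary score = 2*v*/56. Weight score = 2.8*v*/78.4, or (2.8*v* + 1.4)/78.4 with one application on the visit day.

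| Visit 4 | Diary | Weight, none on visit day | Weight, one on visit day |
|---|---|---|---|
| Day 26 | 52/56 = 92.9% | 72.8/78.4 = 92.9% | 74.2/78.4 = 94.6% |
| Day 28 | 56/56 = 100.0% | 78.4/78.4 = 100.0% | 79.8/78.4 = 101.8% |
| Day 30 | 60/56 = 107.1% | 84.0/78.4 = 107.1% | 85.4/78.4 = 108.9% |

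One application on Day 0 instead of two lowers every entry by 1/56 = 1.8 points. Read the other way, a subject seen on Day 30 can miss 60 − 56 = 4 diary-recorded doses and still score 100%. Visits outside the window are kept as recorded (SAP 6.5.10), so 92.9% and 108.9% are not hard limits.

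**Early stoppers.** Someone who takes every dose for 14 full days and then stops scores 39.2/78.4 = 50.0%; for 20 days, 56.0/78.4 = 71.4%. The diary measure gives the same values (28/56 and 40/56).

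**Per-protocol cut-off.** Half of 78.4 g is 39.2 g. As a share of scheduled use this is 39.2/72.8 = 53.8% or 39.2/74.2 = 52.8% for a Day 26 visit, and 39.2/84.0 = 46.7% or 39.2/85.4 = 45.9% for a Day 30 visit (without and with a visit-day application).

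**After matching the days.** Diaries: 52/52, 56/56 and 60/60, all 100%. Capping both sides at SAP Day 28 or the day before Visit 4, whichever comes first, gives 52/52, 56/56 and 56/56. Weight per calendar day with one visit-day application: 74.2/27 = 2.75 g, 79.8/29 = 2.75 g and 85.4/31 = 2.75 g, which is 98.1% to 98.4% of 2.8 g wherever the visit falls.

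**The case against.** No number in the plan is miscalculated. The regimen is 28 days, so net weight over 78.4 g is a legitimate, disclosed measure: the share of the planned course that was used. The per-day sentence describes a different quantity and does not contradict the formula. Compliance enters no model or test. The visit window is the same in all arms of a blinded, randomized trial, so visit timing alone gives no evident bias between arms. Dispensing dates, return dates and dose times are listed, so a determined reader could separate duration from adherence. All of this stands. It limits the consequence, but it does not explain a count of up to 60 diaries over 56 described as available, or a per-day figure with no place in the outputs.

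Dividing everything by the subject's own days also has a cost. Someone who quits on Day 3 would score 100%. Because SAP 7.5.1 gives unreturned kits a return weight of 0 g, a subject who stops after 7 days and keeps both 30 ml bottles would score at least 60/19.6 = 306%, against 60/78.4 = 76.5% on the fixed denominator (assuming 1 g/ml and ignoring bottle weight). This is accepted and shapes the fix.

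Three stronger readings are tempting:

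- A reader might infer that a perfectly adherent subject can score below half. That requires stopping before 14 full days, and the low score is then correct as a share of the planned amount.
- A reader might apply the 16.7% dropout rate to the treatment period and conclude that an arm's mean compliance is materially depressed, or differs between arms. That rate covers loss before completing the study, and completion runs to Week 8 (Protocol 11.6; Table 14.1.1.1, footnote 7). The documents give no dropout rate for the treatment period and none by arm.
- A reader might infer that the per-protocol set is distorted. It already requires a completed Week 4 visit (SAP 7.2.5), and no fully adherent in-window completer comes near 39.2 g.

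**Conclusion.** The mismatch is real and limited in scope. For completers seen within the window who miss nothing, the diary score runs from 92.9% to 107.1% with visit day alone. The weight score runs from about 93% to 109%, the upper end including one application on the visit day. Both ranges assume two applications on Day 0. Early stoppers' scores cannot be read as adherence without their days on treatment. The consequence is confined to the descriptive compliance summary in Table 14.3.5 and its listings. The per-protocol threshold shifts by only a few points of scheduled use, and the primary analysis is untouched. The documents do not establish a between-arm bias. The change is worth making because the rule yields scores above 100% by construction and omits a figure that the same section describes.

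**What to change.** 1. **Diary compliance.** Make numerator and denominator cover the same days. Either use 2 × the days from first dose to the day before Visit 4 (to last dose for early stoppers), or cap both at the earlier of SAP Day 28 and the day before Visit 4, as SAP 6.5.3 does for the itch scores.
2. **Weight per day.** Add to Table 14.3.5 the row that 7.5.1 describes: net weight divided by days on treatment, set against 2.8 g. Define days on treatment, and flag or exclude subjects with unreturned kits imputed as 0 g.
3. **Planned amount.** Keep net weight/78.4 g for the per-protocol rule, so membership does not change. Relabel it *percent of planned 28-day amount* and show days on treatment beside it. The same column guards against an early quitter's high diary score being misread.
4. **Reconciliation.** The sponsor should reconcile the 28-day course in Protocol 8.7 with use until the Week 4 visit in 8.6, since the two differ when that visit moves.

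The cost is SAP and table-shell wording and a few lines of programming. SAP 7.5.1 already takes first and last exposure dates from the EDC, so no new data are needed.
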